4.2. Duration of Study

The anticipated time for study enrollment is 3 months. The duration of study participation is anticipated to be a maximum of 155 days per subject. Subjects will have a total of 13 study visits. The maximum anticipated duration for the study is approximately 8 months.

5. STUDY ENTRY CRITERIA

5.1. Inclusion Criteria

Subjects must meet all of the following criteria to be considered for participation in this study.

- 1. Subject is able to comprehend and is willing to sign an informed consent/assent for participation in this study.
- 2. Male or female ≥ 8 years old.
- 3. Subject has a clinical diagnosis of common warts.
- 4. Subject has up to 1 Target Wart and up to 3 additional Non-Target Warts located on the trunk or extremities. The identified Target and Non-Target Warts must meet the requirements as defined below:
 - a. Each wart must have a longest axis that is \ge 3mm and \le 8 mm and have a thickness of \le 3mm
 - b. Each wart must be a discrete lesion
 - c. Each wart must be present for at least 4 weeks
 - d. Not be covered with hair which, in the investigator's opinion, would interfere with the study medication treatment or the study evaluations
 - e. Not be in an intertriginous fold
 - f. Be the only common wart present when the circular cutout template is centered over the wart
- 5. The Target and Non-Target Warts must have a $PWA \ge 2$
- 6. Subject chemistry and complete blood count results are within normal limits. If any of the laboratory values are outside normal range, the treating investigator must assess the value/s as NOT clinically significant and document this in the subject's medical chart in order for the subject to be eligible for randomization.
- 7. Women of childbearing potential (WOCBP) must have a negative urine pregnancy test within 14 days of the first application of study drug and agree to use an active method of birth control for the duration of the study.
- 8. Subject is non-pregnant and non-lactating.

- 9. Subject is in good general health and free of any known disease state or physical condition which, in the investigator's opinion, might impair the evaluation of any Target and Non-Target Warts or which exposes the subject to an unacceptable risk by study participation.
- 10. Subject is willing and able to follow all study instructions and to attend all study visits.

5.2. Exclusion Criteria

Subjects are excluded from this study if any 1 or more of the following criteria is met:

- 1. Subject has clinically atypical warts on the trunk or extremities.
- 2. Subject is immunocompromised (e.g., due to chemotherapy, systemic steroids, genetic immunodeficiency, transplant status, etc.)
- 3. Subject has periungual, subungual, genital, anal, mosaic, plantar, flat, or filiform wart as a Target or Non-Target Wart
- 4. Subject has a history of Human Immunodeficiency Virus (HIV) infection
- 5. Subject has had any Human Papilloma Virus (HPV) vaccine within 1 year prior to Visit 2
- 6. Subject has used any of the following intralesional therapies within the specified period prior to Visit 2
 - a. Immunotherapy (e.g., *Candida* antigen, mumps antigen, *Trichophyton* antigen); 8 weeks
 - b. Anti-metabolite therapy (e.g., bleomycin, 5-fluorouracil); 8 weeks
- 7. Subject has used any of the following systemic therapies within the specified period prior to Visit 2:
 - a. Immunomodulatory/immunosuppressant therapy (e.g., etanercept,
 - alefacept, infliximab); 16 weeks
 - b. Glucocorticosteroids (inhaled and intra-nasal steroids are permitted); 28 days
- 8. Subject has used any of the following topical therapies within the specified period prior to Visit 2 on, or in a proximity to any Target or Non-Target Warts, that in the investigator's opinion interferes with the study medication treatment or the study assessments:
 - a. LASER, light or other energy based therapy (e.g., intense pulsed light [IPL], photo-dynamic therapy [PDT]; 180 days
 - b. Immunotherapy (e.g., imiquimod, squaric acid dibutyl ester[SADBE], etc.) 12 weeks
 - c. Liquid nitrogen, electrodesiccation, curettage; 60 days
 - d. Hydrogen peroxide; 90 days
 - e. Anti-metabolite therapy (e.g., 5-fluorouracil); 8 weeks
 - f. Retinoids; 90 days
 - g. Over-the-counter (OTC) wart therapies; 28 days
- 9. Subject currently has or has had any of the following within the specified period prior to Visit 1 on or in a proximity to any Target or Non-Target Warts that, in the investigator's opinion, interferes with the study medication treatment or the study assessments:
 - a. Cutaneous malignancy; 180 days
 - b. Sunburn; currently
 - c. Pre-malignancy (e.g., actinic keratosis); currently
- 10. Subject has a history of sensitivity to any of the ingredients in the study medications.

- 11. Subject has any current skin disease (e.g., psoriasis, atopic dermatitis, eczema, sun damage), or condition (e.g., sunburn, excessive hair, open wounds) that, in the opinion of the investigator, might put the subject at undue risk by study participation or interfere with the study conduct or evaluations.
- 12. Participation in another therapeutic investigational drug trial in which administration of an investigational study medication occurred with 30 days prior to Visit 1.

5.3. Removal of Patients from Study Therapy

A subject may be removed from the study therapy for a variety of reasons, including:

- Unacceptable adverse event
- Subject unwilling or refusal to continue with the protocol defined study visits and/or consent/assent withdrawal for study participation
- Change in compliance with an inclusion/exclusion criteria
- Use of a prohibited medication (through Visit 13)
- Pregnancy
- General or specific changes in the subject's condition that render the subject unacceptable for further treatment in this study in the judgement of the investigator.

If a subject is to be withdrawn from the study, the Aclaris Therapeutics, Inc. study monitor or designee must be informed within 24 hours of the decision to remove the subject from the study.

The study may be discontinued at the discretion of Aclaris Therapeutics, Inc. Some examples of reasons for discontinuation are the occurrence of the following:

- Increased frequency, severity or duration of known AEs
- Medical, regulatory or ethical reasons affecting the continued performance of the study
- Difficulties in the recruitment of subjects.

5.4. Withdrawal Procedures

If a subject withdraws from the study prior to Visit 13, the reason for and the date of withdrawal from the study must be recorded on the eCRF. If the reason for withdrawal is an adverse event or a clinically significant abnormal laboratory test result, monitoring of the subject will continue until the event has resolved or stabilized, until the patient is referred to the care of a local health care professional, or until a determination of a cause unrelated to the study drug or study procedure is made.

5.5. Subject Replacement

If a subject is randomized to the study but does not receive a dose of study drug, then the subject will be replaced.

Subjects that are determined to be screen failures may be rescreened for the study and if determined to be eligible for the study they may be randomized using the same subject identifier.

Page 19 of 53 Amendment 2 Version 3 Date: 05 December 2017

5.6. Subject Identifier (SI)

The investigator or designee will assign a unique five-digit subject identifier (SI) to each subject at Visit 1.

The SI format will be NN-NNN where the first 2 digits are the investigational center site number (using leading zeroes, as appropriate). The final 3 digits are the subject number and must be assigned in ascending numerical order, without omitting or repeating any number, starting with 001 at each investigational center. For example, the SI for the second subject that signs an informed consent/assent at site number 04 would be 04-002.

The subject will be identified using the SI in all study documentation for the duration of the study.

6. STUDY PROCEDURES

The schedule of study activities (including assessments, tests, exams, disease assessments, and study drug administration) beginning with screening and continuing through the end of study are outlined in Table 1. A written, signed informed consent form (ICF)/assent must be obtained from each subject prior to performing any study related procedure (e.g., vital signs, clinical laboratory sampling, urine pregnancy test or photography).

Table 1:Study Procedures

Visit	V1	V2	V3	V4	V5	V6	V7	V8	V9	V10	V11	V12	V13
	Screening												
Treatment Day	-13 to 0	1	8	15	22	29	36	43	50	57	78	106	134
Treatment Window	N/A	N/A	±1 day	±4 days	± 4	± 4	±4 days	± 4	± 4	+4	±7	±7	+7
					days	days		days	days	days	days	days	days
Study Procedures													
Informed Consent/Assent	Х												
Inclusion	Х	X^1											
Criteria/Exclusion Criteria													
Subject Identifier	X ²												
Medical	Х												
history/demographics													
Fitzpatrick Skin Type	X ³												
Assessment													
Vital Signs	X ⁴								Х				Х
Prior	X ⁵												
Medications/Therapies													
Clinical Chemistry and	Х								Х				Х
CBC ⁶													
Urine Pregnancy Test ⁷	Х	Х							Х				Х
Target Wart Identification ⁸	Х												
Physician's Wart	Х	Х	Х	Х	Х	Х	Х	Х	Х	Х	Х	Х	Х
Assessment ⁹													
Target Wart Dimensions ¹⁰	Х	Х	Х	Х	Х	Х	Х	Х	Х	Х	Х	Х	Х
Standardized	Х	Х		Х					Х	Х			Х
Photography ¹¹													
Subject Randomization		X ¹²											
Local Skin Reactions		X ¹³	Х	Х	Х	Х	Х						
Study Medication		Х	Х	Х	Х	Х	Х	Х	Х				
Application ¹⁴													
Weighing of Study		Х	Х	Х	Х	Х	Х	Х	Х				
Medication Applicators ¹⁵													
Subject Instructions	Х	Х	Х	Х	Х	Х	Х	Х	Х	Х	Х	Х	
-	1												

Page 21 of 53 Amendment 2 Version 3 Date: 05 December 2017

Concomitant therapies ¹⁶	Х	Х	Х	Х	Х	Х	Х	Х	Х	Х	Х	Х
Adverse Events ¹⁷	Х	Х	Х	Х	Х	Х	Х	Х	Х	Х		

¹Subject inclusion/exclusion criteria will be re-assessed prior to randomization during Visit 2.

²Investigational sites will assign a unique five-digit subject identifier to each subject at Visit 1. This subject identifier will be used in all study documentation for the duration of the study.

³Each subject's skin must be assessed during Visit 1 using the Fitzpatrick Skin Type Assessment. Refer to Section 9.5.1 for the scale.

⁴Vital signs [including temperature, pulse, respiratory rate, blood pressure, height and weight (Visit 1 only)] will be measured by a qualified staff member at Visit 1, Visit 9 and Visit 13.

⁵Prior medications/therapies will be collected for a time-period of 13 days prior to Visit 2. Refer to Section 7.8 for a list of permitted and restricted concomitant medications.

⁶A complete blood count (including hematocrit, hemoglobin, platelet count, red blood cell count and morphology, white blood cell count and differential (absolute and %) including basophils, eosinophils, lymphocytes, monocytes and neutrophils and a clinical chemistry panel including albumin, alkaline phosphatase, alanine aminotransferase (ALT), aspartate aminotransferase (AST), blood urea nitrogen (BUN), bicarbonate, calcium, chloride, creatinine, glucose, lactate dehydrogenase (LDH), phosphorus, potassium, sodium, total bilirubin, total protein, and uric acid.

⁷ Woman of child bearing potential will be required to have a urine pregnancy test at Visit 1, at Visit 2 prior to randomization, Visit 9 and Visit 13.

⁸The treating investigator will identify 1 Target Wart and up to 3 additional Non-Target Warts on the trunk and extremities.

⁹ The investigator will use the Physician Wart Assessment (PWA) to assess each Target and Non-Target Warts. The investigator must assess the Target and Non-Target Warts prior to application of the study medication at Visit 2-Visit 9. In order to be eligible for randomization at Visit 2, the subject must have a PWA grade ≥ 2 .

¹⁰ The investigator will measure the dimensions (longest diameter and thickness) of the Target and Non-Target Warts at Visit 1 and prior to randomization at Visit 2. In order for the subject to be randomized at Visit 2 each Target and Non-Target Wart must have the specific dimensions outlined in Section 8.1. At Visits 3-13 the investigator will measure the diameter of each Target and Non-Target Wart.

¹¹ At Visits 1, Visit 2 (prior to study medication application), Visit 4 prior to study medication application, Visit 9, Visit 10 and at Visit 13, a qualified investigational center staff member will take a photograph of each Target and Non-Target Wart using the Aclaris supplied camera. All photographs will be sent to a central imaging laboratory.

¹² Subjects will be randomized at Visit 2 prior to application of study medication. Investigational study staff will re-confirm subject eligibility prior to randomization.

¹³ The investigator and subject will assess each Target Wart for local skin reactions associated with irritation at Visits 2-13. At Visit 2-Visit 9, the investigator and subject will assess the Target and Non-Target Warts for LSRs prior to the application of the study medication. The subject will assess LSRs 10 (\pm 4) minutes after the application of A-101 study medication and the investigator will assess for LSRs 20 (\pm 4) minutes after application of A-101 study medication. Refer to Section 9.1 for the complete list of Local Skin Reaction signs and symptoms.

¹⁴The investigator will apply the A-101 study medication to subject 8 to 17 years of age. Subjects 18 years of age and older will apply their A-101 study medication in the presence of the treating physician or a member of the investigational study staff that has been trained on the protocol. All Target and Non-Target Warts will be treated with study medication following randomization at Visit 2. If a Target or Non-Target Wart meets the criteria for re-treatment as defined in Section 7.6 the lesion will be re-treated at Visit 3-9. Following application of study medication, subjects must NOT wash/submerge the Target or Non-Target Warts for at least 6 hours and they must NOT apply any topical products to the Target or Non-Target Warts for at least 6 hours.

Page 22 of 53 Amendment 2 Version 3 Date: 05 December 2017 ¹⁵Sites will be required to weigh all A-101 study medication applicators before and after treatment and document the weight of each applicator in the subject's eCRF.

¹⁶All concomitant therapies including (topical and oral) prescription medications, over the counter medications and natural supplements and non-drug therapies including chiropractic, physical therapy, and energy based therapy must be documented in the subject CRF. Subjects must not apply any topical products (e.g., moisturizers, sunscreen, etc.) to their Target or Non-Target Warts within 12 hours prior to any study visit.

¹⁷The reporting period for Serious Adverse Events (SAEs) begins when the subject signs the informed consent and continues through Visit 11. Refer to Section 10.1.2 for instructions on the reporting of SAEs. Non-serious clinical adverse events will be collected following the application of the study medication at Visit 2. Non-serious adverse events that occur between the time of consent and study medication application will be documented as medical history. All safety reporting (AEs and SAEs) will conclude at Visit 11 (approximately 28 days after last study medication application) except for clinical adverse events related to local skin reactions.

Page 23 of 53 Amendment 2 Version 3 Date: 05 December 2017

7. STUDY TREATMENT

7.1. Investigational Study Medication

The study medications for the study are A-101 45%, and matching Vehicle. All study medications are solutions that are water-clear, colorless solutions which are indistinguishable in physical appearance.

Table 2Study Medication Information

Study Medication	A-101 45%	Vehicle					
Name							
Manufacturer	James Alexander Co	rporation, Blairstown NJ					
A-101 concentration	45 0						
(%)							
Pharmaceutical Form	Sc	lution					
Storage Conditions	Storage Conditions 15°C to 25°C or 59°F to 77°F protected from excessive heat, open and combustibles, out of direct sunlight and in a well-ventilated area*						
Route	Topical						
Frequency	A-101 Study Medication will be applied once a week for 8 week						
Application	Safety glasses and nitrile or vinyl examination gloves must be worn						
	during the application proce	ss. Latex gloves are prohibited.					
Duration of	Apply study medication to e	ach Target/Non-Target Wart for					
Administration	approximately 15 seconds. Allo	ow each Target/Non-Target Wart to					
	remain undisturbed for appro	ximately 15 seconds. Repeat the					
	application/waiting cycle until the	study medication has been applied to					
	each Target and Non-	Target Wart up to 3 times.					
Activated Applicators	Activated applicators are stable for	or 4 hours at room temperature (15°C					
	to 25°C or	[•] 59°F to 77°F)					

*Excursions from these temperature ranges must be reported to Aclaris.

7.2. Subject Randomization

Prior to the start of the study, Aclaris Therapeutics, Inc./designee will generate a randomization list that will be provided to the assigned clinical packaging organization for study medication labeling.

The randomization list will be stored with limited access to designated personnel for study medication labeling.

Subjects will be randomized to the study in a 1:1 ratio. Subjects will be randomized at Visit 2 following re-confirmation of subject eligibility.

Page 24 of 53 Amendment 2 Version 3 Date: 05 December 2017

7.3. Study medication packaging, storage and dispensing

A-101 45% and matching Vehicle will be provided by Aclaris Therapeutics, Inc. and labelled according to the local law and legislation.

The study medication will be packaged in single use applicators. Each single-use applicator consists of a crushable glass ampoule that contains 2.2 milliliters (mL) of study medication that provides for at least 1.3 mL of study medication available for treatment. The ampoule is provided inside a sealed polyethylene tube with a flocked, doe foot applicator on one end.

Each subject kit will be packaged with 10 treatment applicators. The outside of each subject kit will be labelled with a two part, three panel, double blind label. One part (one-panel) of the label remains attached to the Subject Kit, the other part (two-panel tear-off) is separated and attached to the subject's Label Page CRF when the subject is randomized.

A-101 study medication must be stored in a location where there is limited access to the investigational study medication at room temperature (15°C to 25°C or 59°F to 77°F) protected from excessive heat, open flame and combustibles, out of direct sunlight and in a well-ventilated, dry area.

Investigational study medication supplies are only to be used for subjects properly consented and randomized to this study.

7.4. Drug Accountability

The investigator or designee will maintain an accurate record of the receipt of the study medications as shipped by Aclaris Therapeutics, Inc. (or designee), including the date received and the condition of the study medications. One copy of this receipt will be returned to Aclaris Therapeutics, Inc. (or designee) when the contents of the study medication shipment have been verified and one copy maintained in the study file. In addition, an accurate study medication disposition record will be kept, specifying the amount dispensed for each subject and the date of dispensing. This inventory record will be available for inspection at any time. At the completion of the study, the original inventory record will be available for review by Aclaris Therapeutics, Inc. upon request.

Final drug accountability will be completed by the study monitor at the completion of the study and all unused study medication will be returned to Aclaris Therapeutics, Inc. drug depot for disposal per Aclaris Therapeutics, Inc. (or designee's) written instructions.

7.5. Weighing of Study Medication Applicators

Sites will be required to weigh each A-101 study medication applicator before all Target and Non-Target Warts are treated. The used applicators will be weighed again after all warts have been treated. The weight of the applicators will be documented in the subject's eCRF. Sites will be supplied with a scale to weigh each applicator.

Page 25 of 53 Amendment 2 Version 3 Date: 05 December 2017

7.6. Study Medication Treatment

The study medications are for external, topical use on the Target and Non-Target Warts on the appropriate study subject only.

The investigational center staff member must comply with the study medication storage conditions outlined in Section 7.1.

At Visit 2, the investigational study staff will select the appropriate study medication applicator for treatment of a specific subject. Subjects ages 18 years of age and older will apply the appropriately labeled A-101 study medication to all Target and Non-Target Warts in the presence of the treating investigator or investigational staff that has been trained on the protocol. Investigational study staff will apply A-101 study medication to subjects between the ages of 8 and 17.

At Visit 3-9, any Target or Non-Target Wart that has a PWA grade of >0 and ONLY Target Warts or Non-Target Warts that have a PWA grade of >0, must receive study medication treatment UNLESS either of the following criteria apply to the Target or Non-Target Wart:

- The Target or the Non-Target Wart has a pre-treatment LSR grade of 3 (severe) for any sign or symptom AND the grade has increased compared to the previous visit.
- The Target or the Non-Target Wart is, in the investigator's opinion, not appropriate for a retreatment (the investigator must note the reason on the subject's Comments CRF page).
- The Target or the Non-Target Wart, in the Investigator's opinion, cannot be visualized so the Investigator cannot assess the PWA.

Following treatment with the A-101 study medication applicator, all used applicators must be disposed of in a biohazardous container.

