7.6.1. Preparing the Study Medication for Application

To perform a study medication treatment for Target and Non-Target Warts a staff member will select the appropriate study medication applicator. The following instructions outline the procedure for application of the study medication to the Target and Non-Target Warts:

- Investigational Study Staff member will prepare the A-101 study medication applicator for all subjects, regardless of age by:
 - Washing their hands prior to, and after completing the study medication treatments
 - Wear safety glasses and nitrile or vinyl examination gloves during the treatment; latex gloves are prohibited
 - Complete the study medication applicator label as instructed
 - Visually inspect the applicator for damage:
 - If the applicator appears damaged do not use it for the treatment, contact the study monitor for disposal instructions and select another unused applicator for treatment.

Page 26 of 53 Amendment 2 Version 3 Date: 05 December 2017

If the applicator is intact, proceed with the applicator preparation process as outlined in Figure 1.

Step 1: Hold the Study Medication applicator so that the applicator cap is pointing up.

Step 2: Crush the ampule in the applicator by applying pressure at the center of the barrel of the applicator.

sleeve.

Step 3: Remove the cardboard Step 4: Tap the barrel of the applicator to ensure the solution is free of the crushed ampule.

Page 27 of 53 Amendment 2 Version 3 Date: 05 December 2017

Figure 1: Diagram Showing the Process for Preparing A-101 Study Medication

7.6.2. Applying Study Medication to Target and Non-Target Warts on the Trunk and Extremities

Subjects that are between the ages of 8 and 17 will have their A-101 study medication applied by the investigational study staff and the staff will follow the application process outlined below for all Target and Non-Target Warts.

Subjects 18 years of age and older will apply their A-101 study medication to his/her identified Target and Non-Target Warts in the presence of the treating physician or member of the investigational staff.

The following instructions will be used by all individuals applying A-101 study medication to all Target and Non-Target Warts:

- Do not apply the study medications to eyes, nose, mouth, mucous membranes, or open wounds
- Thoroughly cleanse the Target and Non-Target Warts by firmly rubbing with a swab/wipe wetted with 70% isopropyl alcohol

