9.1. Local Skin Reactions (LSR)

The LSR assessment is the Investigator's assessment of the signs and the subject's assessment of the symptoms associated with irritation at the Target/Non-Target Wart site (*i.e.*, the Target/Non-Target Wart and the skin immediately surrounding the Target/Non-Target Wart exposed to study medication). The Investigator may refer to previous photographs to assist with these assessments only after the PWA has been performed.

The Local Skin Reaction signs to be assessed are:

- Erythema
- Edema
- Erosion
- Ulceration
- Vesicles/bullae
- Excoriations
- Scabbing.

The Local Skin Reaction symptoms to be assessed (by the Subject) are:

- Stinging/burning
- Pruritus (itch).

At Visits 2-13, the Investigator will evaluate the LSR signs at the Target/Non-Target Wart site(s) as follows:

- At visits where a study medication treatment or retreatment is performed:
 - \circ Perform an LSR assessment prior to any study medication application
 - $\circ~$ For treated Target and Non-Target Warts perform an LSR assessment 20 (±4) minutes after the Treatment Completion Time.

At Visits 2-13, the Subject will assess the LSR symptoms at the Target/Non-Target Wart site(s) as follows:

- At visits where a study medication treatment or retreatment is performed:
 - Perform an LSR assessment prior to any study medication application
 - For every treated Target and Non-Target Wart site, 10 (±4) minutes after the Treatment Completion Time, report the average of the severity of the LSR for all symptoms since completion of the study medication treatment.
 - At visits where no study medication treatment is performed:
 - Perform an LSR assessment.

The Investigator and subject should report the one integer that best describes the severity of each LSR sign or LSR symptom for the Target and Non-Target Wart sites using the scale below.

Page 36 of 53 Amendment 2 Version 3 Date: 05 December 2017
Local Skin Reactions			
Grade	Descriptor		
0	None		
1	Mild		
2	Moderate		
3	Severe		

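### Table 1 marks local skin reaction assessments only at Visits 2–7 although the text requires Visits 2–13, and the retreatment rule in 7.6 is not reconciled with the open-wound prohibition in 7.6.2

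*Protocol*

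**What the plan says.** **Assessment schedule.** In Table 1 of the protocol (Section 6) and of the SAP (Section 4), the row "Local Skin Reactions" is marked at Visits 2 to 7 and blank from Visit 8. Footnote 13, attached to that row, calls for assessment at Visits 2–13 and adds that at Visits 2–9 "the investigator and subject will assess the Target and Non-Target Warts for LSRs prior to the application of the study medication". Protocol 9.1 and SAP 6.1 also give Visits 2–13, once for investigator-rated signs and once for subject-rated symptoms.

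**Retreatment rule (protocol 7.6).** At Visits 3–9 a wart with PWA above 0 "must receive study medication treatment UNLESS either of the following criteria apply to the Target or Non-Target Wart". Three exceptions follow:

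1. The wart has a "pre-treatment LSR grade of 3 (severe) for any sign or symptom AND the grade has increased compared to the previous visit".
2. The wart "is, in the investigator's opinion, not appropriate for a retreatment", with the reason noted on the Comments page of the CRF.
3. The wart, "in the Investigator's opinion, cannot be visualized so the Investigator cannot assess the PWA".

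**Application instructions (protocol 7.6.2).** Everyone who applies the medication is told: "Do not apply the study medications to eyes, nose, mouth, mucous membranes, or open wounds".

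**What is graded (protocol 9.1).** The sentence "The Local Skin Reaction signs to be assessed are" introduces a list that includes erosion, ulceration and excoriations, each scored from 0 (none) to 3 (severe).

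**The concern.** Two things do not fit together.

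First, the schedule contradicts itself. The hold in 7.6 depends on a pre-treatment LSR grade at every retreatment visit, yet the Table 1 marks stop at Visit 7. Coordinators often work from the schedule table. One who did so here, without its footnote, would have no grade at the last two treatment visits and would record no LSRs during follow-up. SAP 8.5 summarises LSR scores by visit and treatment group. Footnote 17 of Table 1 also exempts adverse events related to local skin reactions from the cut-off of safety reporting at Visit 11. Both suggest that later LSR data are wanted.

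Second, 7.6 and 7.6.2 each bear on whether damaged skin is treated, and neither refers to the other. Section 7.6 makes treatment the default and leaves most reactions to opinion. Section 7.6.2 is a flat prohibition that does not appear among the 7.6 exceptions. Two sites acting in good faith could handle the same eroded wart differently. That would change the number of applications received before the primary endpoint at Visit 10. The Per-Protocol population excludes subjects who missed more than 3 treatment visits, and neither document says whether an attended visit with the application withheld counts as missed.

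**Working it through.** The plan states no figure on this point, so the check compares the texts and counts.

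**1. Schedule.** Inputs: the Table 1 LSR row, footnote 13, protocol 9.1 (SAP 6.1) and the visits to which 7.6 applies.

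| Visits | Table 1 LSR mark | Footnote 13 and 9.1 | Pre-treatment grade needed by 7.6 |
|---|---|---|---|
| 2 | yes | yes | no (first treatment) |
| 3–7 | yes | yes | yes (5 visits) |
| 8–9 | no | yes | yes (2 visits) |
| 10–13 | no | yes | no (follow-up, 4 visits) |

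- Required by the text: Visits 2–13, which is 12 visits.
- Marked in the table: Visits 2–7, which is 6 visits. Unmarked: 12 − 6 = 6.
- Retreatment visits: Visits 3–9, which is 7. Unmarked among them: 7 − 5 = 2.
- Follow-up visits without a mark: 4 of 4.

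The gap is the same in both documents. In the same tables the PWA row is marked at all 13 visits and the medication row at Visits 2–9, so a general loss of marks on the right-hand side is unlikely.

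**2. Reach of the automatic hold.** Take one LSR sign and list each pair of previous-visit grade and current pre-treatment grade, both 0 to 3.

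- All pairs: 4 × 4 = 16.
- Current grade 1 or more: 4 × 3 = 12.
- Automatic hold (current grade 3 and higher than before): 0→3, 1→3 and 2→3, which is 3.
- No automatic hold: 12 − 3 = 9. These are the 4 × 2 = 8 pairs with a current grade of 1 or 2, and the one persistent severe pair, 3→3.

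In those 9 pairs treatment remains the default unless the investigator uses the second exception or the wart cannot be visualised. The pairs carry no frequencies, so 9 of 12 describes the scope of the rule and is not a rate.

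**3. Does 7.6.2 oppose 7.6 in those pairs?** It would have to treat a graded erosion, ulceration or excoriation as an open wound. Section 7.6.2 mentions no LSR grade, and 9.1 grades the signs without mentioning wounds. The only other use of the term is as an example of an excluded skin condition at entry (exclusion criterion 11). The link is never made or denied.

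**4. Comparator.** At treatment visits LSRs are graded before application and again afterwards (subject at 10 minutes, investigator at 20 minutes). Suppose a sign is 0 before and 3 after application at one visit, and 3 before application at the next. Against the earlier pre-application grade this is an increase (0→3) and the hold applies. Against the post-application grade it is not (3→3). Section 7.6 does not say which is meant.

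**The case against.** A reader might infer that 7.6 orders treatment of eroded or ulcerated warts while 7.6.2 forbids it, so that sites receive opposite mandatory instructions. The documents do not support that, for three reasons.

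- The second exception in 7.6 lets the investigator withhold treatment from any wart judged unsuitable. A site that sees an open wound can satisfy both sections by using it. No grade pair makes treatment unconditionally mandatory. Section 8.3 adds a further hold when a reaction such as edema or scabbing hides the wart.
- The direct contradiction depends on equating a graded erosion, ulceration or excoriation with an open wound, which no section does. The nine pairs without an automatic hold therefore cannot be counted as nine conflicts.
- For a persistent grade 3 reaction without a skin break, 7.6.2 says nothing. Releasing the automatic hold when the grade has not risen is a feature of the rule, not a contradiction.

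A reader might also infer that the effect falls mainly on the active arm. Protocol 2.2 calls reactions in the previous study generally transient and gives no rates by arm, so that is conjecture.

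On the schedule, the sponsor could say that footnote 13 hangs on the LSR row and settles the matter, so no careful site would be without a grade. That is fair, and it limits the harm to sites reading the marks alone. It does not make the table right. Comparing pre-treatment grade with pre-treatment grade is likewise the natural reading of 7.6, so the comparator is a missing detail rather than an error.

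These arguments remove the stronger reading. The inconsistent marks and the missing link between 7.6 and 7.6.2 stand.

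**Conclusion.** The schedule is wrong as written in both documents. Six of the 12 visits at which the text requires LSRs carry no mark in Table 1; two of the six are retreatment visits where 7.6 needs the grade, and four are follow-up. This assumes that the printed tables match their extracted text, which the identical pattern in both documents supports.

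Sections 7.6 and 7.6.2 are not reconciled. One makes retreatment the default, with an automatic LSR hold only for a grade 3 that has increased; the other prohibits application to open wounds; and the term is not tied to the graded signs. Investigator discretion lets a site comply with both, so this is a failure to reconcile.

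The effect on exposure, safety data or the Visit 10 result cannot be sized, because the documents give no frequency of reactions or withheld applications. The corrections are worth making because they concern an operative safety schedule and a treatment rule. They do not call the design or the primary analysis into question.

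**What to change.** - Mark the LSR row of Table 1 at Visits 8–13 in the protocol and the SAP, to match footnote 13, protocol 9.1 and SAP 6.1.
- Have the sponsor reconcile protocol 7.6, 7.6.2 and 9.1 so that one instruction applies, including whether a graded erosion, ulceration or excoriation counts as an open wound. Which clinical rule is right is not for this review, and none is proposed.
- In the same edit, state whether the previous-visit comparator in 7.6 is the pre-application or the post-application grade, and correct the lead-in, which is worded for two criteria although three follow.
- Optional: summarise withheld applications by reason, visit and arm, for example with SAP Table 14.3.1. Reasons already go on the Comments page and into a listing, so this adds convenience rather than filling a gap in collection.

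The cost is two table corrections, a short protocol amendment with a note to sites and, if wanted, one summary table. No visits or staff are added beyond what the text already requires. Depending on how the sponsor reconciles the sections, some applications may be given or withheld differently from present practice.
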